Appendix 1F - Additional IV Medication for BP Use in China

The drugs listed in this Appendix are additional medications for BP lowering that can be used in China sites.

1. Suggested IV medication for BP lowering

1) Esmolol

Dosage and administration:

Bolus or infusion: It is recommended that an initial loading dose of 0.5 milligrams/kg body weight (500 micrograms/kg) infused over a one-minute duration, followed by a maintenance infusion of 0.05 milligrams/kg/min (50 micrograms/kg/min) for the next 4 minutes. If it is efficacious, the maintenance infusion may be continued at 0.05 mg/kg/min. If an adequate therapeutic effect is not observed, repeat the same loading dosage and follow with a maintenance infusion. The maintenance infusion may be continued at 0.05 mg/kg/min or increased step wise (e.g. 0.1 mg/kg/min, 0.15 mg/kg/min or a maximum of 0.2 mg/kg/min) with each step being maintained for 4 or more minutes. The maintenance infusion may be increased to a maximum of 0.3 mg/kg/min. Maintenance dosages above 200 µg/kg/min (0.2 mg/kg/min) have not been shown to have significantly increased benefits.

2) Enalaprilat

Dosage and administration:

Therapy should be individualised. For patients on diuretic therapy, the dosage of enalaprilat should be reduced. Dose in hypertension is 1.25 mg every six hours administered intravenously over a five minute period. Doses higher than 5 mg every six hours are not suggested.

2. IV medication for BP lowering which can also be used

1) Diltiazem

Dosage and administration:

An initial dose of 10 mg or 0.5 mg - 0.25 mg/kg body weight infused within 3 minutes can be used. Diltiazem should be diluted in normal or glucose solutions to a concentration of 1% before use. This dose can be repeated after 15 minutes. A maintenance infusion of 5 µg - 15 µg/min is also permitted.

2) Nitroglyceride

Dosage and administration:

Nitroglyceride injection 10 mg is diluted in 0.9% normal solution 500 ml or 5% glucose solution 500 ml. The initial dose of nitroglyceride is 5 drops/min, and under close BP monitoring may increase by 5 drops/min every 3-5 minutes. If the dose of 20 drops/min is still not efficacious, 10 drops/min can be added every 3-5 minutes. Doses usually can be from 5 to 50 drops/min.

Note: Phosphodiesterase inhibitors must not be used with GTN.

3) Nimodipine

Dosage and administration:

Nimodipine 50 ml/50 mg should be put in a micro pump and infused in a constant speed 4 ml/hour, once a day. Usually it can be used for 5 to 14 days. Then, change to oral nimodipine. However, the BP lowering effect of oral nimodopine is not obvious.

4) Frusemide

Dosage and administration:

The usual initial dose of furosemide is 20-80 mg. If needed, the same dose can be repeated every 2 hours. The total dosage cannot be more than 1 g/d. If it is not effective, the dose should not be increased, to avoid renal toxicity.

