I.v. treatment protocols, based on available medications, are provided in Appendixes 1A to 1F. The i.v. treatment will be titrated against regular BP monitoring to achieve a target systolic BP range (100-120 mmHg) within 3 hours after successful reperfusion with MT. It is anticipated that i.v. control of systolic BP will be required for at least several hours.

Oral treatment protocol

The switch from i.v. to oral BP lowering treatment will be made at the discretion of the responsible physician, depending upon the control and stability of the BP and the clinical status of the patient. It is anticipated that oral treatment will be started by 24 hours.

The oral treatment protocol will also include a defined strategy for titration of treatment to achieve effective early systolic BP control once oral treatment is commenced. If the patient is unable to swallow, treatment should be administered via nasogastric tube.

For the intervention group, the goal is to maintain systolic BP levels <120 mmHg for at least 72 hours of hospital stay. If the patient is transferred to another hospital facility within 72 hours, then attempts should be made to continue therapy to achieve the systolic BP target of <120mmHg. The target systolic BP after hospital discharge remains 130/140 mmHg, as guideline-based recommendations for second stroke prevention. BP levels will be reviewed at 90 days follow-up and medication adjusted as necessary to maintain systolic BP <130/140 mmHg as per contemporary guidelines.

Control group (higher BP target)

Patients allocated to the control group will receive management of BP to maintain systolic BP 140-180mmHg. Appendix 1G outlines the protocol for control patients. For this group, the attending clinician should stop BP lowering treatment if the systolic BP is ≤ 150 mmHg in order to maintain a higher BP target level of 140-180 mmHg comparing to intensive group. The oral and i.v. agents used will be the same as in the intensive BP lowering group as detailed in Appendixes 1A to 1G. Oral antihypertensive therapy may be started at any time the treating physician feels the patient is stable. Oral therapy must be started by Day 7. The target systolic BP after hospital discharge is <130/140 mmHg, as per contemporary guideline-based recommendations for high risk cardiovascular disease patients.

Discontinuation of allocated management

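### Protocol Appendix 1F prints the weight-based diltiazem bolus as a descending, half-labelled range, so its ceiling could be 0.25 or 0.5 mg/kg

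*Protocol*

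**What the plan says.** Protocol section 6.7 makes the appendices the working instructions for intravenous treatment: "I.v. treatment protocols, based on available medications, are provided in Appendixes 1A to 1F". The same section says that control patients receive the same agents as the intensive group. Appendix 1F adds further drugs for China: "The drugs listed in this Appendix are additional medications for BP lowering that can be used in China sites". Diltiazem is in the second of its two tiers, the agents that may also be used.

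The diltiazem entry has three dosing statements:

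- Initial bolus: "An initial dose of 10 mg or 0.5 mg - 0.25 mg/kg body weight infused within 3 minutes can be used".
- Repeat: "This dose can be repeated after 15 minutes".
- Maintenance: "A maintenance infusion of 5 µg - 15 µg/min is also permitted".

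Diltiazem is dosed nowhere else in the protocol or SAP, and no single-dose or daily maximum is printed for it.

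**The concern.** The weight-based bolus is malformed in two ways. It runs from the larger number down to the smaller, and the per-kilogram unit is attached only to the second number. Every other dose range in Appendices 1A to 1F ascends. The esmolol entry on the same page shows that the authors could write a weight-based dose clearly: it gives 0.5 mg/kg and repeats it in micrograms per kilogram.

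What is at stake is the first dose that a clinician draws up. The drug is a blood-pressure-lowering bolus for patients who have just been reperfused, and the line is operative in both arms. Because the bolus may be repeated after 15 minutes, any misreading carries into the second dose. Several other agents have a printed cap, for example labetalol (300 mg in 24 hours, Appendix 1C), clevidipine (32 mg/h, Appendix 1E) and frusemide (1 g/day, Appendix 1F). For diltiazem, this unclear line is the only limit on the bolus.

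**Working it through.** **Inputs**

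- Flat dose 10 mg, weight-based figures 0.5 and 0.25, infusion within 3 minutes, repeat after 15 minutes: Protocol Appendix 1F.
- Body weight: not in the documents. I assume 60-80 kg and show 50-100 kg as a wider range.

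The plan states no ceiling in mg, so there is no figure of its own to reproduce. The check is to list the readings that the printed text allows and compare their maxima.

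**Readings**

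1. *Both numbers are per kilogram and the order is reversed.* The range is 0.25-0.5 mg/kg and the maximum is 0.5 mg/kg. In favour: the maintenance line of the same entry also puts its denominator only after the second number, so the missing unit on the first number is weak evidence by itself. Against: 10 mg equals 0.25 mg/kg at 10 / 0.25 = 40 kg, so for anyone heavier the flat alternative falls below the whole weight-based range.
2. *0.5 mg is an absolute dose.* The maximum is 0.25 mg/kg. Against: the bottom of the range is then 0.5 / 10 = one-twentieth of the flat dose in the same sentence, which is implausible.
3. *0.5 is a misprint for a per-kilogram figure below 0.25.* The maximum is again 0.25 mg/kg. This restores the ascending order, but the printed number is then wrong.

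**Size of the difference**

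Ratio of the two ceilings: 0.5 / 0.25 = 2, at any body weight.

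Largest single bolus = ceiling × weight; total after one repeat = 2 × that bolus.

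| Weight | Bolus at 0.25 mg/kg | Bolus at 0.5 mg/kg | After one repeat, 0.25 | After one repeat, 0.5 |
|---|---|---|---|---|
| 50 kg | 12.5 mg | 25 mg | 25 mg | 50 mg |
| 60 kg | 15 mg | 30 mg | 30 mg | 60 mg |
| 70 kg | 17.5 mg | 35 mg | 35 mg | 70 mg |
| 80 kg | 20 mg | 40 mg | 40 mg | 80 mg |
| 100 kg | 25 mg | 50 mg | 50 mg | 100 mg |

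Against the flat 10 mg, at 60-80 kg:

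- Ceiling 0.25 mg/kg: 15/10 = 1.5 to 20/10 = 2 times.
- Ceiling 0.5 mg/kg: 30/10 = 3 to 40/10 = 4 times.

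**Do the safeguards settle the dose?**

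Section 6.7 stops therapy at a systolic pressure of 100 mmHg in the intensive group. Appendix 1G allows treatment of controls only above 150 mmHg. Appendices 1A to 1E require continuous heart-rate monitoring, with blood pressure and heart rate recorded every 5 minutes during active treatment. These rules govern whether to treat and when to stop. None of them says how large the first bolus should be. Section 6.10.5 schedules the post-bolus recheck at 5 and 15 minutes, by which time a bolus infused within 3 minutes has been given in full.

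**The case against.** The strongest case on the other side has five parts.

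- **Text conversion.** A single lost character could turn an ascending range into the printed one, and the fault would then not be in the plan. This cannot be excluded. However, the line is running prose and the neighbouring decimals in Appendix 1F read cleanly. The point limits confidence and makes a look at the original page the first step.
- **The two ceilings are not exhaustive.** Once a misprint is admitted, the second number could be the wrong one, and the true maximum could be neither figure. This stands. The factor of 2 is the spread between readings of the printed figures and does not bound what was intended.
- **Low exposure.** Diltiazem is second-tier, permitted and not required, and listed only for China sites. The clear 10 mg option comes first in the same sentence. Section 6.7 requires locally available and approved agents and lets clinicians modify treatment on judgement. Nothing shows that any site used the higher dose. All of this is true. It lowers the priority but does not tell a site what the weight-based dose is.
- **Recheck timing.** Any bolus in the protocol is in before its scheduled recheck, and continuous heart-rate monitoring runs during the injection. The timing is therefore not specific to diltiazem. It shows only that the recheck cannot replace a clear first dose.
- **No effect on inference.** The trial compares blood pressure targets, not agents, and no statistical quantity changes. This is agreed: the matter is dosing clarity and patient safety.

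**Conclusion.** The concern holds. As printed, the weight-based diltiazem bolus has no determinate ceiling. The readings that the text allows give 0.25 or 0.5 mg/kg, a twofold difference at any weight, or 15-20 mg against 30-40 mg per bolus at an assumed 60-80 kg. The internal evidence points both ways and the documents do not show which was meant, so no corrected figure can be derived from them.

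Confidence is medium. The conclusion assumes that the text was converted faithfully and that at least one of the two printed numbers is the intended per-kilogram maximum. The line should be corrected because it is an operative dosing instruction, but the practical exposure is small and the analysis is untouched.

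**What to change.** 1. Check the original page. If it shows a clear ascending range, nothing in the plan needs to change.
2. If the wording is as printed, issue a minor amendment and a site notice that keep only the flat dose for now: initial diltiazem dose 10 mg, infused within 3 minutes. The existing rule on repeating after 15 minutes then refers to 10 mg. This uses a dose already in the protocol and invents none.
3. Restore a weight-based option when the clinical leads issue one ascending range with mg/kg on both ends, verified against the source document or product label.

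The cost is a small wording amendment, a notice to China sites, and temporary loss of an optional alternative for a second-tier drug. Randomisation, sample size, alpha and all analyses stay as they are.

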17. APPENDIX

Appendix 1 - BP management protocol

Appendix 1A - BP protocol for centres with Urapidil (China)

Intensive BP lowering group	TREATMENT PROTOCOL
INITIAL therapy	
BP Target	SBP <120mmHg achieved within 1 hour after randomisation
Monitoring	
 Continuous HR monitoring Record BP/HR q 5 mins during active treatment, then q 15 min for first hour, q 30 min for next 5 hours and then hourly to 24 h
Urapidil (IV)	
 If SBP \geq 120 mmHg and HR >55 bpm, repeat 10-25 mg IV bolus q5 mins until target SBP reached (<120mmHg) or HR <55 bpm If HR increases by >15 bpm or is >90 bpm, add IV beta blocker
Hydralazine (IV)	
 Hydralazine test dose: 5 mg IV bolus over 1 minute If SBP \geq 120 mmHg, repeat 5 mg IV bolus in 5 minutes If SBP still \geq 120mmHg, give 10 mg IV bolus q 5 mins until target SBP reached Increase to 20 mg bolus if required Maximum hydralazine dose = 240mg
Glyceryl Trinitrate (topical)	
If BP persistently \geq 120 mmHg:
 
 ADD topical glyceryl trinitrate (paste or patch) at a rate of 5-10 mg/24 hour 
(\approx 200-400 μg/hour). NB: also known as topical nitroglycerin

Continuous IV Infusions (requires ICU admission)	
If BP persistently \geq 120 mmHg:
 
 Urapidil infusion 5-30 mg/hour If target still not reached ADD infusion of hydralazine 50-150 μg/min OR glyceryl trinitrate 1-100 μg/Kg/min
MAINTENANCE therapy	
BP Target	Maintenance of SBP 100-120 mmHg
Monitoring	Once SBP is under target (confirmed by 4 readings 15 minutes apart): 
 Record BP/HR q 30 minutes for 5 hours and then q 1 h for 18 h
IV treatment prn	
If SBP exceeds 120mmHg at any point:
 
 Give Urapidil (10-25 mg) and/or hydralazine (10-20 mg) boluses. BP and HR should then be recorded 5 and 15 minutes later If SBP is 100-120mmHg, Urapidil 10-25 mg (dose dependent on initial response) should be administered q 6 hours for the first 24 hours after symptom onset (total of 3 doses) If SBP \leq 100 mmHg, cease therapy If HR increases by >15 bpm or is >90 bpm, add IV beta blocker Note: urapidil and hydralazine may be used together during the maintenance phase

Oral treatment

Start treatment by 24 hours (use nasogastric if required)

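### The China appendices give unreconciled i.v. glyceryl trinitrate dosing: the ceiling in Appendices 1A and 1B is at least 50 times the usual top rate in Appendix 1F

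*Protocol*

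**What the plan says.** Section 6.7 (I.v. treatment protocol) sends sites to Appendixes 1A to 1F according to the drugs they have. Three of these are marked for China.

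- **Appendices 1A (urapidil) and 1B (phentolamine).** If SBP stays at or above 120 mmHg, the row for continuous infusions, which requires ICU admission, starts with the centre's own drug. A second infusion follows if that fails. In 1A the line begins "If target still not reached ADD infusion of hydralazine 50-150" (micrograms/min) and continues "OR glyceryl trinitrate 1-100", with the unit micrograms/kg/min. The abbreviation keys to 1A and 1B spell the unit out per kilogram, so it is not an artefact of text extraction. Neither appendix gives a concentration, starting rate or step for GTN.
- **Appendix 1F.** Its scope is stated as: "The drugs listed in this Appendix are additional medications for BP lowering that can be used in China sites". GTN, there called nitroglyceride, is in the second list, headed "IV medication for BP lowering which can also be used". The preparation is: "Nitroglyceride injection 10 mg is diluted in 0.9% normal solution 500 ml or 5% glucose solution 500 ml". On rate: "The initial dose of nitroglyceride is 5 drops/min", raised in steps of 5 drops/min under close BP monitoring. Above 20 drops/min, if the effect is still inadequate, "10 drops/min can be added every 3-5 minutes". The entry ends: "Doses usually can be from 5 to 50 drops/min". The note beneath it calls the drug GTN. No drop factor is given.

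Appendices 1C, 1D and 1E carry the same range of 1 to 100 micrograms/kg/min but are not labelled for China.

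**The concern.** A China site can hold two schedules for one intravenous vasodilator, in different units, and no text says which governs. Appendix 1F presents its drugs as additional, yet an i.v. GTN infusion is already in 1A and 1B. Once both are put in micrograms/min, the top of one lies far above the usual top of the other. The intensive arm aims for SBP below 120 mmHg within one hour, and Section 7.2.3 uses severe hypotension in that arm as its own example of an excess of events that would lead to amending or stopping the study. Staff setting an infusion rate need one consistent upper figure.

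**Working it through.** The plan states no converted figure to reproduce, so the check is a unit conversion.

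**Inputs from the protocol:** 10 mg in 500 ml, and 5 to 50 drops/min (1F); 1 to 100 micrograms/kg/min (1A, 1B).

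**Assumed, because the documents give neither:** body weight W of 50 to 90 kg, and drop factor D of 10 to 60 drops/ml. The reference case is 70 kg and 20 drops/ml.

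**1. Concentration in 1F.** 10,000 micrograms / 500 ml = 20 micrograms/ml.

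**2. Usual range in 1F.** Rate = (drops/min) / D × 20.

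- D = 10: 10 to 100 micrograms/min
- D = 20: 5 to 50 micrograms/min
- D = 60: 1.7 to 16.7 micrograms/min

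**3. Range in 1A/1B.** Rate = (micrograms/kg/min) × W.

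- 50 kg: 50 to 5000 micrograms/min
- 70 kg: 70 to 7000 micrograms/min
- 90 kg: 90 to 9000 micrograms/min

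**4. Ratio of the upper ends.** 100W / (50/D × 20) = W × D / 10.

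| Weight | D = 10 | D = 20 | D = 60 |
|---|---|---|---|
| 50 kg | 50 | 100 | 300 |
| 70 kg | 70 | 140 | 420 |
| 90 kg | 90 | 180 | 540 |

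The smallest value is 5000 / 100 = 50. The reference case is 7000 / 50 = 140.

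**5. Overlap at the lower end.** The 1A/1B floor is W micrograms/min and the usual top rate in 1F is 1000/D, so the ranges meet only if W × D ≤ 1000. At 10 drops/ml the floor (50 to 90) lies inside the 1F range (10 to 100). At 20 drops/ml the ranges just touch at 50 kg and are separate above that. At 60 drops/ml they are separate at every weight considered.

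**6. Allowing for the open end of 1F.** With the fastest steps, every 3 minutes, three steps of 5 take the rate from 5 to 20 drops/min in 9 minutes. Steps of 10 for the rest of one hour give 20 + 10 × (60 − 9)/3 = 190 drops/min. That is 190 micrograms/min at 20 drops/ml and 380 at 10 drops/ml. The 1A/1B ceiling is still 7000 / 190 = 36.8 times higher in the reference case, and at least 5000 / 380 = 13.2 times higher over the assumed ranges.

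**7. A possible unit slip.** Read without the per-kilogram term, 1 to 100 micrograms/min would contain the whole usual range of 1F at each drop factor in step 2. The hydralazine infusion on the same line is in plain micrograms/min.

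**The case against.** The strongest reply is that these are not two conflicting limits. For nitroglyceride, 1F gives a usual range after a step rule with no stop. Where 1F wants a cap it states one, as for esmolol (0.3 mg/kg/min) and frusemide (1 g/day). This stands: a reader might infer two hard maxima, and the documents support only one stated ceiling and one usual range. The mismatch remains, because step 6 shows that an hour of the fastest 1F titration still falls well short.

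Second, the 140-fold figure rests on a weight and a drop factor that the protocol does not give. This also stands, so the figure to rely on is the minimum of 50 over the stated ranges.

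Third, the practical hazard is small. In 1A and 1B the GTN infusion is a late add-on, tried after boluses, topical treatment and a first infusion. It requires ICU admission, with BP and heart rate recorded every 5 minutes during active treatment. Therapy ceases at SBP 100 mmHg, 1F asks for close BP monitoring, and Section 6.7 leaves clinicians free to modify treatment. All of this stands and lowers the priority. It does not tell staff which range applies.

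Fourth, the two appendices could be meant for different settings, an ICU step and a second-list drug. Nothing in the protocol gives that as a reason for different doses.

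A reader might also infer that 100 micrograms/kg/min is simply a typing error. Step 7 makes a unit slip plausible, but the documents do not prove it. Nor do they combine the 1A/1B rate with the 1F dilution, so figures built on that combination would describe a situation that the protocol does not create.

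**Conclusion.** The inconsistency is real. For China sites, the stated GTN ceiling in Appendices 1A and 1B is at least 50 times the usual top rate in Appendix 1F over 50 to 90 kg and 10 to 60 drops/ml, and 140 times at 70 kg and 20 drops/ml. Weight and drop factor are assumptions, but no combination in those ranges brings the upper ends together. The disagreement concerns the upper end; any overlap is confined to the bottom of the 1A/1B range. The documents do not settle which schedule is right. Because the ceiling is unlikely to be reached, this is a patient-safety correction that should be made, not evidence of an imminent hazard or a flaw in the trial's inference. Sample size and analysis are untouched. The demonstrated inconsistency is limited to the China appendices; 1C to 1E matter only because they repeat the same entry.

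**What to change.** The clinical and pharmacy leads should verify the GTN infusion entry and replace it in 1A, 1B and 1F with one range in micrograms/min. It should give the starting rate, step, maximum, concentration, and a drop factor or pump rate. They should check the identical entry in 1C to 1E at the same time and notify sites.

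Until this is verified, China sites should start with the lower 1F schedule, using a stated drop factor or pump rate, and should not titrate toward 100 micrograms/kg/min. This is a precaution and does not imply that the 1F figures have been shown to be correct.

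The cost is an appendix correction and a site letter. There is no statistical cost.

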Appendix 1G – Control group-higher BP target

RANDOMISED GROUP	TREATMENT
CONTROL - HIGHER BP TARGET	
Use acute intravenous therapy if SBP >180 mmHg, and stop BP lowering agents when SBP \leq 150 mmHg;
 
Any BP lowering treatment could be used ONLY if SBP >150 mmHg and maintain a SBP range 140-180 mmHg
 
Oral anti-hypertensives and/or topical nitrates can be used when patient medically stable, as assessed by responsible clinician. Oral treatment should be started by discharge / transfer (use nasogastric if required).
 
 • If not contraindicated and no other drug is specifically required, start combination therapy ACEI + diuretic therapy in addition to previous anti-hypertensives

Key to abbreviations:

ACEI – Angiotensin converting enzyme inhibitor; SBP – systolic blood pressure

Appendix 2 – Recommendation for MT devices

MT is the background treatment in this trial. All devices listed below (including but not limited to), which are approved by China Food and Drug Administration (CFDA) during the study period, are recommended as first-line devices for MT.

Device name	Manufacturer	Description
Aspiration catheter		
ACE	Penumbra	Aspiration catheter
Retriever		
Solitaire	Medtronic	Stent Retriever
Trevo	Stryker	Stent Retriever
Revive	Cerenovous	Stent Retriever
Aperioa	Acandis	Stent Retriever
Reco	Minitech Medical	Stent Retriever

